8.7.7 Overall Survival

Overall survival (OS) is defined as the interval from the date of first dose of investigational agent until the date of death.

OS in months is calculated as:

- (date of death, or censoring date of first dosing + 1) / 30.4375
- Where the censoring rules are specified as following:
- For subjects who have not died, OS will be censored at last contact date.
- Median OS will be provided (estimated using K-M estimate, with 95% CI) and Kaplan-Meier curve of OS will be plotted for Safety Analysis Set.

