5.1.5 Survival Follow-up

Subjects who discontinue study treatment will be followed for survival by phone contact every 3 months. Survival follow-up will continue until death, for up to 2 years, or until study closure. Subjects will also be followed for initiation of another cancer therapy.

If a subject withdraws from the interventional portion of a study and does not consent to continued follow-up of associated clinical outcome information, the investigator will not access for purposes related to the study the subject's medical record or other confidential records requiring the subject's consent. However, investigators will consult public records, such as obituaries and the Social Security index to establish survival status.

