6.6 Handling of Partial Dates for Adverse Events

When determining treatment-emergent adverse events (TEAEs), partial dates will be handled as follows.

- If the day of the month is missing, the onset day will be set to the first day of the month unless it is the same month and year as study treatment. In this case, the onset date will be assumed to be the first dose date of treatment.
- If the onset day and month are both missing, the day and month will be assumed to be 1 January, unless the event occurred in the same year as the study treatment. In this case, the event onset will be coded to the first dose date of treatment to conservatively report the event as treatment-emergent.
- A missing onset date will be coded as the first dose date of treatment. If the resulting onset date is after a reported date of resolution, the onset date will be set equal to the date of resolution.
- A partially missing resolution date will be conservatively imputed as the latest date in the range of missing date element(s) (for example 2020-10-31 if the date is 2020-10-UNK), date of last dose + 90 days, day of study discontinuation, or death, whichever comes first.

Data listings will present the partial date as recorded in the electronic case report form (eCRF).

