6.9 Handling of Partial Dates for Other Data

Other data (such as disease history) with partial dates will be listed as collected. For calculation of time intervals, the dates will be imputed with the first day of the month (if the day is missing) or with 1 January (if both day and month are missing).

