6.10 Handling of Missing Data

Missing data will not be imputed, except for:

- Missing date parts, i.e., partial dates, discussed above
- Missing AEs grade severity and relationship to study drug of AEs, discussed in Section 8.6.2.
- Missing efficacy assessments discussed in Section 8.7.

Confidential Page 15 of 30

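### SAP 8.7.7 has no rule for a partial death date, and the residual rule in SAP 6.9 can date a death before last contact, a new therapy or first dose

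*SAP*

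**What the plan says.** SAP 8.7.7 states that OS "is defined as the interval from the date of first dose of investigational agent until the date of death". Its only further date rule concerns survivors: "For subjects who have not died, OS will be censored at last contact date". It does not say what to do when a death date is incomplete.

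SAP Section 6 handles partial dates by data type: adverse events (6.6), medications (6.7), procedures (6.8) and everything else (6.9). SAP 6.9 opens with "Other data (such as disease history) with partial dates will be listed as collected" and then, for time intervals, says that "the dates will be imputed with the first day of the month (if the day is missing) or with 1 January" if the month is missing too. SAP 6.10 keeps this in force by listing "Missing date parts, i.e., partial dates, discussed above" among the exceptions to its rule against imputation.

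The neighbouring sections check imputed dates against known ones. SAP 6.6 moves an adverse event onset in the dosing month to the first dose date and adds: "If the resulting onset date is after a reported date of resolution, the onset date will be set equal to the date of resolution". SAP 6.7 requires an imputed medication start to precede its end date. For anti-cancer medication taken after study treatment, it uses the latest possible start, limited by the end date. SAP 6.9 has no such check.

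Protocol 6.4.2.2 censors OS at the time last known alive and also has no partial death date rule.

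**The concern.** A death date is not an adverse event date, a medication date or a procedure date, and OS is a time interval, so SAP 6.9 is the only section whose wording reaches it. Its rule suits disease history, where a missing day usually costs little. For a death it has two defects. It can only move the date earlier or leave it unchanged. It also ignores what is already known about the subject, namely that he or she had been dosed and was alive on a later day.

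The same date is used elsewhere:
- **PFS and DOR (SAP 8.7.6, 8.7.2):** death is an event only within 90 days of the last tumor assessment, and deaths after a new anti-cancer therapy are disregarded.
- **Death tables and listings (SAP 8.6.2):** deaths are split into on-treatment and survival follow-up, and days from first and last dose are listed.
- **Adverse event duration (SAP 6.6):** a partial resolution date is capped at death.

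An impossible survival time would also force an unplanned decision once the data have been seen.

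**Working it through.** The plan gives no figure to reproduce here, so the check applies SAP 6.9 to the OS formula and looks at the results.

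**1. Formula.** SAP 8.7.7, read with the minus sign that the PDF text drops:

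OS (months) = (date of death − date of first dose + 1) / 30.4375.

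**2. Examples.** All dates are assumed. First dose is 16 March 2020.

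| Death recorded as | Last known alive | Date under 6.9 | Day count | OS (months) | Days before last known alive |
|---|---|---|---|---|---|
| March 2020 | 25 Mar 2020 | 1 Mar 2020 | −15 + 1 = −14 | −0.46 | 24 |
| September 2020 | 20 Sep 2020 | 1 Sep 2020 | 169 + 1 = 170 | 5.59 | 19 |
| 2020 | 20 Sep 2020 | 1 Jan 2020 | −75 + 1 = −74 | −2.43 | 263 |
| 2021 | 20 Sep 2021 | 1 Jan 2021 | 291 + 1 = 292 | 9.59 | 262 |

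**3. When each fault occurs.** Zero or negative OS needs a death recorded in the calendar month of first dose (day missing) or the calendar year of first dose (day and month missing). A death before last known alive needs a last contact in the recorded month or year, after the imputed day. The extreme values are:
- Day missing, first dose on the 31st: (1 − 31 + 1)/30.4375 = −0.95 month.
- Day and month missing, first dose on 31 December: (−364 + 1)/30.4375 = −11.93 months.

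**4. Shift per imputed death.** With deaths spread evenly over a 365-day year:
- A missing day moves the date earlier by 0 to 30 days, mean 14.7 days (14.7/30.4375 = 0.48 month).
- A missing day and month moves it by 0 to 364 days, mean 182 days (182/30.4375 = 6.0 months).

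**5. PFS and DOR.** Two further examples with assumed dates:
- A new therapy and a death are both recorded only as September 2020. SAP 6.7 puts the therapy on 30 September (absent an earlier end date), and SAP 6.9 puts the death on 1 September. Even a complete therapy date of 10 September leaves the order reversed. A death that the SAP says to disregard can then count as an event.
- Last tumor assessment is 15 June 2020 and the true death is 24 September 2020, a gap of 15 + 31 + 31 + 24 = 101 days, so the subject is censored. Recorded as September 2020, the death becomes 1 September, a gap of 78 days, and the subject becomes an event.

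**6. Effect on the median.** The documents give no count of partial death dates, so this is a simulation with assumed inputs: 60 subjects (the Phase 2 maximum in SAP 3.2), exponential OS with median 8 months, 2-year follow-up.

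| Partial death dates (assumed) | Shift in median OS (months) | Subjects with OS ≤ 0 |
|---|---|---|
| 10-20% month-only | about −0.04 to −0.10 | about 0.5 (at 20%) |
| 20% month-only + 5% year-only | −0.31 | 1.6 |
| 20% month-only + 10% year-only | −0.54 | 2.7 |

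If software drops non-positive times in the last two settings, those deaths are lost and the median rises by about 0.1 month instead. The sampling standard deviation of the median in this set-up is about 1.5 months.

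**The case against.** The case for leaving this alone has several parts.

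- **SAP 6.9 never mentions death.** Its one example is disease history, so the rule reaches death only as a residual clause. This stands as a limit on how firmly the point can be put. It does not remove the gap: if 6.9 was not meant for deaths, the SAP has no death date rule at all, and the same sentence is needed.
- **Early deaths are closely recorded.** Protocol 5.8.6.2.2 and 5.11 have deaths within 90 days of study drug reported as SAEs, and SAEs are due within 24 hours. A month-only date gives non-positive OS only for a death in the month of first dose, which falls inside that window. This stands and makes that case less likely, though not impossible.
- **Public records have a narrow role.** Protocol 5.1.5 says "investigators will consult public records, such as obituaries and the Social Security index to establish survival status", but only for subjects who withdraw and decline continued follow-up. Others are phoned every 3 months, which makes year-only dates hard to assume. This stands. The documents do not say that either source yields partial dates.
- **The stakes are low.** OS is secondary and descriptive, SAP 3.2 says the sample size is not inferential, and the month-only shift is small beside sampling error. This stands and settles the severity.

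A reader might infer that reported median OS will be too short by 0.3 to 0.5 month. The documents do not support that. The figure depends on a 5-10% year-only rate for which they give no basis, and the direction for the median reverses if non-positive times are dropped.

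**Conclusion.** The point holds as a minor correction. On the plain text of SAP 6.9, a partial death date takes its earliest possible value with no floor. It can therefore precede the date last known alive, a new anti-cancer therapy that came first, or the first dose. One partial date in the relevant month or year is enough; these orderings follow from the rule and need no assumed frequency.

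The size is uncertain because the number of partial death dates is unknown. With month-only gaps in 10-20% of deaths, under the assumed survival model, median OS moves by about 0.1 month or less. Anything larger requires year-only dates and remains an assumption. No test or error rate depends on OS. The practical harm is impossible individual times, possible misclassification of deaths in PFS, DOR and the death tables, and an ad hoc choice at analysis.

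**What to change.** Exempt death dates from SAP 6.9 and add a rule to 8.7.7. A partial death date is imputed within the recorded month or year, no earlier than the later of the first dose date and the day after last known alive, and no later than the date the death was reported. The SAP should name which date inside these bounds is used and what happens if no date satisfies all of them. Use the same date for OS, PFS, DOR and the death tables, flag imputed dates in listings, and state how a wholly missing death date is handled.

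Taking the earliest date allowed by the lower bounds, the four examples give OS of 0.36, 6.24, 6.24 and 18.23 months, in place of −0.46, 5.59, −2.43 and 9.59.

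The upper bound matters. A mid-year rule without one could date a death after it was known: last alive 1 February 2020, a May 2020 call reports a death in 2020, and the rule assigns 1 July. The floor should use the date last known alive, since a last contact might be the call that reported the death.

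The cost is a few sentences in the SAP and a few lines of code. Last contact is already needed for censoring; the sponsor should confirm that the date each death was reported is on the database.

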8.8 Pharmacokinetic Parameters

PK analyses will be conducted according to separate Pharmacokinetic Analysis Plan.

